### *Adipose tissue microdialysis*

During the OGTT without GLP-1 infusion, a microdialysis catheter will be inserted into abdominal subcutaneous adipose tissue using local anesthesia and sterile technique. At the start of the OGTT, the microdialysis pump containing T1 perfusion fluid (M Dialysis) will be infused at 1  $\mu$ l/min. After 60 minutes the microdialysate will be discarded and a fresh microdialysate sample will be obtained over 90 minutes. Samples will be collected on ice and stored at -80° C until analysis.

### *Hyperglycemic clamp*

After an overnight fast, pre-HCT patients will undergo a hyperglycemic clamp procedure, as described by DeFronzo *et. al.* and by our collaborators (37, 38). Arterialized blood will be collected by using a heating pad after insertion of a venous catheter (39). Baseline values for glucose, insulin, C-peptide, and glucagon will be calculated by averaging the measurements obtained at -20, -10, and -1 minute before initiation of the glucose infusion. At time 0, a 200 mg/kg priming dose of 20% dextrose (Hospira) will be given for 10 minutes. Thereafter, blood glucose will be measured approximately every 5 minutes and plasma glucose will be maintained at 200 mg/dL with a variable infusion of 20% dextrose solution for 150 minutes (37, 38). Insulin, C-peptide, and glucagon will be measured 3 times during the first 10 minutes, and then every 10 minutes from 90 to 120 minutes. At time 120 minutes, 5 gm of the secretagogue L-arginine will be injected over 1 minute while the patient is hyperglycemic (40). Insulin, C-peptide, and glucagon levels will be measured 3 times from time 120-130 minutes and then every 10 minutes from 130 to 150 minutes. At 150 minutes the glucose infusion and the procedure will be stopped.

The clamp, 2 OGTTs, and microdialysis procedure will be repeated after HCT between day+80 to +100 (+/- 10 days). Patients diagnosed with PTDM requiring treatment after HCT will be maintained on short-acting insulin which will be held the morning of the studies. Oral antidiabetes medications are not routinely used at our HCT center, however if prescribed, these agents will be washed out for 5 days prior to the procedure and the patient will be maintained on short-acting insulin as above.

### *Calculations*

First-phase GSIS will be calculated in 2 ways: 1) the difference between the maximum plasma insulin level during the first 10 minutes and the average of the 3 baseline insulin values ( $\Delta\text{Insulin}_{0-10}$ ) or 2) as the AUC for insulin above baseline value from time= 0 to 10 minutes ( $\text{AUC}_{\Delta\text{Insulin}0-10}$ ). Second or late-phase GSIS will be calculated in the same manner but from time 90-120 minutes (37). These analyses will be repeated using C-peptide and glucagon measurements. Maximum hormone secretion will be determined by the acute insulin, C-peptide, and glucagon response to L-arginine ( $\text{AIR}_{\text{arg}}$ ,  $\text{ACR}_{\text{arg}}$ , and  $\text{AGR}_{\text{arg}}$ , respectively). These values will be calculated as the mean hormone level for the first 10 minutes after arginine stimulation minus their average baseline levels (37).

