**Subaim 1A. To determine if a compensatory increase in glucose stimulated insulin secretion (GSIS) by  $\beta$ -cells precedes PTDM development in patients without diabetes undergoing MRD HCT.** Based on our C-peptide and oral glucose tolerance test (OGTT) data, we hypothesize that PTDM-prone individuals maintain euglycemia pre-transplant via enhanced  $\beta$ -cell secretory capacity followed by progressive  $\beta$ -cell dysfunction and relative insulin insufficiency after transplant. In a prospective MRD HCT cohort without diabetes,  $\beta$ -cell function and secretory capacity will be directly measured with hyperglycemic clamps before and 90 days after transplant.

**Subaim 1B. To determine if excess glucagon secretion and impaired  $\alpha$ -cell response to glucose or GLP-1 contributes to the hyperglycemia of PTDM.** We will test the hypothesis that PTDM patients have increased glucagon levels and that glucose and GLP-1 induced  $\alpha$ -cell suppression are incomplete. To assess  $\alpha$ -cell dysregulation, glucose-induced glucagon suppression will be measured during a hyperglycemic clamp and during 2 OGTTs either with or without GLP-1 infusion, before and 90 days after HCT.

**Specific Aim 2. To determine if the IL-33/ST2 axis promotes immune/islet cell dysregulation during PTDM.** We hypothesize that PTDM is characterized by decreased protective IL-33/ST2 signaling in adipose tissue at rest (*i.e.* pre-transplant)

followed by increased systemic, inflammatory signaling during stress (*i.e.* post-transplant), which leads to  $\beta$ -cell compensation and exhaustion, respectively. To investigate the ST2 pathway, we will measure adipose and plasma levels of IL-33 and sST2 and quantify ST2 expression on circulating Tregs and Th1 cells before and after HCT from our MRD cohort. IL-33 effects on T cells and on human islet function will be assessed *in vitro*.

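### The clamp glucagon indices reuse insulin's maximum-minus-baseline, which understates a fall, and AGRarg against fasting nets the arginine rise against suppression already present

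*Combined protocol and SAP*

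**What the plan says.** Subaim 1B (Section 1.0) states that "glucose-induced glucagon suppression will be measured during a hyperglycemic clamp". Section 10.2 lists glucagon suppression among the secondary comparisons, both at day +90 and as a change from baseline, but gives no formula. A nadir is mentioned there only for the OGTT.

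The clamp formulas are in Section 6.0, Calculations, and are written for insulin. The first index is "the difference between the maximum plasma insulin level during the first 10 minutes and the average of the 3 baseline insulin values". The second is taken "as the AUC for insulin above baseline value from time= 0 to 10 minutes". Both are applied again at 90-120 minutes. The subsection then says "These analyses will be repeated using C-peptide and glucagon measurements", without changing direction or sign.

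For the response to arginine (AIRarg, ACRarg and AGRarg) the rule is: "These values will be calculated as the mean hormone level for the first 10 minutes after arginine stimulation minus their average baseline levels". The only baseline defined is the fasting one, obtained by "averaging the measurements obtained at -20, -10, and -1 minute before initiation of the glucose infusion". Arginine is injected at 120 minutes, while the patient is hyperglycemic.

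The sampling schedule is "Insulin, C-peptide, and glucagon will be measured 3 times during the first 10 minutes", "and then every 10 minutes from 90 to 120 minutes". That gives three early samples and four late ones (90, 100, 110 and 120 minutes).

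**The concern.** An index that takes the highest sample suits a hormone that rises. Applied to a hormone expected to fall, it selects the least suppressed sample, so sampling noise alone makes suppression look smaller than it was. The text also does not say which of the two indices is the suppression measure named in Section 10.2.

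AGRarg raises a separate difficulty. By 120 minutes glucagon may already be well below fasting. Subtracting the fasting value then mixes two alpha-cell features: how far glucose suppressed glucagon, and how strongly arginine raised it. Subaim 1B hypothesises incomplete suppression in PTDM. If that is right, PTDM patients would appear to have a larger arginine response even when the rise itself is the same.

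**Working it through.** The documents give no clamp glucagon level, variability or power, so there is no stated figure to reproduce. The sample counts and the fasting baseline come from the Hyperglycemic clamp subsection.

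Assumptions: fasting glucagon 60 pg/mL; within-person CV 8/12/20%; independent errors with SD proportional to level; 17 per group for power.

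**1. Late window, four samples.** The expected maximum of four normal values is the mean plus 1.03 SD. For a true fractional fall s from fasting level F:

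maximum index = -sF + 1.03 x CV x (1-s)F.

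- s = 0.30 (fall 18, level 42): the SD is 3.36/5.04/8.40, so the index is -18 + 3.46/5.19/8.65 = -14.5/-12.8/-9.3.
- s = 0.15 (fall 9, level 51): the SD is 4.08/6.12/10.2, so the index is -9 + 4.20/6.30/10.5 = -4.8/-2.7/+1.5.

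As a share of the true fall, the understatement is 1.03 x CV x (1-s)/s, whatever the fasting level. That is 2.40 x CV at a 30% fall (19/29/48%) and 5.83 x CV at a 15% fall (47/70/117%). In simulation (400,000 draws), a true fall of 9 reads as a rise in 11/32/55% of patients with the maximum, against 0.4/4/15% with the window mean.

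**2. Late-window group comparison.** For a 30% v 15% fall with a between-person SD of the fall of 10, power with the maximum v the mean is 66.7 v 67.1, 61.9 v 62.0 and 51.4 v 49.0%. There is no material loss, because the upward shift is similar in both groups. This assumes equal fasting glucagon. Section 3.0 suggests higher fasting glucagon in PTDM. With the same true fall of 18 and assumed fasting levels of 60 v 75-90, the maximum shows a false difference of 1.03 x CV x (15 to 30) = 1.2 to 6.2 pg/mL, and p<0.05 in 6-25% of comparisons. The mean shows about 0, with p<0.05 in about 5%. If error did not grow with level, this would not arise.

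**3. Early window, three samples.** Assume a linear fall reaching 30% v 15% at 10 minutes and a between-person SD of 5. Power (%) at CV 8/12/20%:

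| Sample times (min) | Maximum | Mean | Signed AUC |
|---|---|---|---|
| 3, 6, 10 | 56/41/26 | 91/72/39 | 88/66/34 |
| 2, 5, 10 | 37/28/19 | 87/64/33 | 86/62/31 |

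With a smaller fall (15% v 5%), across both schedules and SD 5 or 10, power is 12-42% with the maximum and 14-59% with the mean.

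The raw contrast does not always shrink. For 30% v 15% at 3, 6, 10 min it is 3.7/4.4/5.3 with the maximum against 5.7 with the mean. For 15% v 5% at CV 20% it is 4.0 against 3.8. In that last case (SD 5) power is 16% with either the maximum or the signed AUC.

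**4. AUC sign.** For a late 30% fall, the signed AUC divided by 30 minutes gives -18.0 at every CV. If only area above baseline counted, the index would be zero in 100/99/85% of patients (about 88/68/45% for a 15% fall).

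**5. AGRarg.** This part is algebra:

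stimulated - fasting = (stimulated - pre-arginine) + (pre-arginine - fasting) = rise - suppression.

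With an assumed rise of 40 in both groups and fasting 60, suppression of 18 v 9 gives 40 - 18 = 22 and 40 - 9 = 31. The difference of 9 is 60 x 0.15; it runs from 6 to 15 for fasting levels of 40 to 100. Against the pre-arginine level the result is 40 v 40.

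**The case against.** The plan calculates each phase in two ways. The subscript on its AUC index denotes the change in insulin, which reads naturally as a signed area, and truncation at zero is nowhere mentioned. A signed AUC performs close to the mean, so the plan may already hold a sound suppression index. This stands. A reader might infer that the plan discards area below baseline, but the documents do not say so. The maximum index is still prescribed for glucagon alongside the AUC, with nothing to say which one is suppression.

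Section 10.2 compares groups and changes over time, and does not test absolute suppression. In the late window the upward shift largely cancels between groups. This also stands. The bias is in the individual values and group means, and late-window power is not a reason to object unless fasting levels differ.

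A reader might infer that the maximum always shrinks the early group contrast. The calculations do not support that: at CV 20% with a small fall, the contrast is slightly larger with the maximum. The early power loss also depends on glucagon actually falling within 10 minutes.

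A fasting-referenced AGRarg is a defined quantity, and the same identity applies to insulin, where AIRarg contains second-phase secretion. This stands, so the documents do not support calling AGRarg or its insulin and C-peptide counterparts invalid. The problem is reading the fasting-referenced value as the arginine response. The Calculations subsection cites a published source that cannot be checked here, but a citation does not replace a stated index.

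**Conclusion.** The point holds for the secondary clamp glucagon measures and should be corrected before analysis. Followed as written, the maximum index understates suppression in both groups. With four late samples the shift is about 1.03 sampling SDs, which at the assumed CVs is 19-48% of a 30% fall and 47-117% of a 15% fall. In the early window it is less efficient than the mean or the signed AUC in most assumed scenarios, provided glucagon is falling. The AGRarg identity needs no assumption; only its size does.

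The upward direction of the late bias follows from taking a maximum. All sizes in pg/mL, percentages and power rest on assumed glucagon levels, CVs, falls and sample times.

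A reader might infer that the Subaim 1B primary result or the sample size is compromised. It is not: Section 10 makes that outcome total glucagon AUC during the OGTT, and no clamp glucagon index enters the sample size calculation.

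**What to change.** Amend Section 6.0, Calculations, in two places.

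1. For glucagon, do not use the maximum index. Define clamp suppression as the signed AUC of change from the fasting baseline, not truncated at zero, over 0-10 and 90-120 minutes. The mean change over 90-120 minutes is the equivalent late measure. Keep the maximum index for insulin and C-peptide only. The AUC is preferable to a plain mean in the early window because it depends less on sample timing: for the same linear 30% fall the mean is -11.4 with samples at 3, 6, 10 min and -10.2 at 2, 5, 10 min, while the signed AUC divided by 10 minutes is -9.0 for both.

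2. Report AGRarg also against the mean of the pre-arginine clamped samples (90-120 minutes, the last taken before the injection), and use that version to interpret the arginine response. Label the fasting-referenced value as net change from fasting. The same additional increment may be reported for AIRarg and ACRarg.

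The cost is a short wording change and slightly more analysis work. The samples are already scheduled; no new samples, assays or patients are needed.

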### *Immune / Metabolic Studies*

In addition to the 6 study visits, this protocol will involve 5 separate blood draws for the patient [pre-transplant, Day +10, Day +20, Day +30, and Day +90 (all +/- 7 days)]. During each blood draw, no more than 50 ml of blood will be drawn for serum and lymphocyte analysis. Aliquots will be analyzed using standard immunologic techniques and by flow cytometry as outlined in the preliminary data section. Blood will be drawn for research purposes at the same time as routine blood sampling. Venous blood will be obtained by accessing the central venous catheter using sterile technique or via peripheral venipuncture. Samples will be coded with a unique alphanumeric identifier at the time of collection so that patient identity will be available only to study investigators and research staff. Codes will be sequential numbers and letters.

Blood samples and database will be maintained indefinitely by the study investigators or the laboratory of [name]/[name] and the research staff. A total of 250 ml of blood will be drawn on 5 occasions for lymphocyte and serum analysis.

#### *Static islet incubation*

Human islets will be obtained from the NIDDK supported, Integrated Islet Distribution Program (<http://iidp.coh.org/>). In this program, pancreatic islets are prepared from cadaver donors by islet isolation centers around the USA. This human tissue can be sent to more than 100 investigators without identifying personal health information. Investigators are unable to track any information related to the pancreas donor. The only information received is gender, age, BMI, and whether or not the donor had diabetes. Because of these factors, this research is generally considered non-human research. After receipt of the de-identified tissue, islet set viability and secretory function will be assessed during exposure to various cytokines including IL-33. Vanderbilt Islet Procurement and Analysis Core will perform islet experiments using standard techniques.

#### *Diagnosis of PTDM*

PTDM is defined by the occurrence of a fasting blood glucose level  $\geq 126$  mg/dL or a random blood glucose level  $\geq 200$  mg/dL at any point from day +1 (day after stem cell infusion) to day +100 after transplant. Fasting blood glucose level will be assessed weekly during routine outpatient visits from day 1 to day 100 after transplant. Patients will be evaluated following an 8 hour overnight fast (water and medications allowed) during standard of care visits. Random blood glucose levels from day +1 to day +100 after transplant will be assessed during standard of care visits or during hospitalization. For hospitalized patients and patients receiving total parenteral nutrition (TPN), all blood glucose determinants will be considered random blood glucose levels for purposes of analysis.

#### *Data Management and Safety*

All data will be collected prospectively until day 100 post-transplant. Information will be stored in a password protected electronic database. After day 100, the database will be updated when the patient is seen in the clinic for their annual visit (i.e. 1 year after transplant). In addition, the standard of care in the transplant program is to discuss complex inpatients and outpatients (within the first 100 days) on a weekly basis. Detailed minutes of these meetings are routinely maintained. Major events (e.g.: unexpected

toxicity and all deaths) are routinely reviewed in a Quality Assurance Meeting and detailed minutes are kept. The above measures will ensure that study patients are monitored closely after transplant and that data will be accurate.

A total of 550 mL of blood will be collected from the patient over approximately 110 days (over 3 to 4 months) for this study.

## **7.0 Risks and Toxicity Management**

### *Risks*

- 1) Study visits at Vanderbilt can be inconvenient
- 2) Venipuncture, blood sampling, and catheter insertion can cause mild discomfort, bruising, and rarely infection
- 3) Repeated blood sampling can worsen anemia, which is monitored frequently after transplant
- 4) Symptoms of hyperglycemia including: thirst, frequent urination, and dry mouth may develop during the hyperglycemic clamp. Symptoms will be monitored closely and minimized by keeping blood glucose levels at 200 mg/dL by adjusting the glucose infusion.
- 5) Arginine is a potent stimulator of insulin and glucagon secretion and will be used during the hyperglycemic clamp. Arginine is commonly employed as a diagnostic test for growth hormone deficiency. It may cause flushing, nausea, or vomiting in about 3% of subjects using doses 6 times the amount used in this study. Since arginine can cause vein irritation, it will be administered by a central venous catheter or large vein to minimize these symptoms.
- 6) GLP-1 [Clinalfa, Bachem (Weil am Rhein, Germany)] will be infused intravenously during the OGTT. GLP-1 can cause nausea, vomiting, headache, and hypoglycemia (usually in patients on combination therapy for diabetes). The dose of GLP-1 in this study is well tolerated and the hormone is rapidly metabolized with a half-life < 2 minutes in the circulation. Thus the effects of GLP-1 should be negligible shortly after stopping the infusion. Based on previous experience, GLP-1 should have no significant side effects at the dose given in this study.

For toxicity attributed to the study, the NCI Common Terminology Criteria for Adverse Events (CTCAE) version 5.0 will be used to characterize the severity.

### *Protection against risk*

- 1) To minimize patient discomfort and venipuncture, blood draws for research purposes will be coordinated with routine clinical blood sampling when possible and will use existing central venous catheters when available
- 2) Nurse or physician will be present during study days

3) Anemia is common after HCT and patients are intensively followed with complete blood counts. Patients routinely receive blood transfusions for a hematocrit <24. Blood for research purposes will not be drawn if hematocrit is known to be <24 and the patient has not yet received transfusion. Once transfusion has been performed, study blood will be drawn.

4) Patients will be monitored closely during study visits and glucose infusions will be adjusted to prevent symptomatic hyperglycemia during hyperglycemic clamps.

5) A unique alphanumeric code will be assigned to each study participant and their study samples to protect their confidentiality. Clinical information and laboratory data will be kept in a password protected database maintained by and accessible to the study investigators and research staff. The key to decode patient identity will be kept in a password-protected database. Only the investigators and research staff will have access to the database.

## **8.0 Reporting of Adverse Events or Unanticipated Problems**

Any untoward medical event will be classified as an adverse event (AE), regardless of its causal relationship with the study. An adverse event will be classified as serious (SAE) if it a) results in death, b) is life-threatening, c) requires inpatient hospitalization or prolongation of existing hospitalization, d) results in persistent or significant disability or incapacity, or e) is a congenital anomaly or birth defect.

Patients undergoing HCT are at high risk for AE's and often require multiple admissions to the hospital during the first 3-4 months after transplantation. For the purposes of this study, only the following SAE's will be reported to the IRB:

-Failure of neutrophil engraftment by day 35 after transplant. Neutrophil engraftment is defined as the first of 3 consecutive days of absolute neutrophil count  $\geq 0.5 \times 10^9/L$ .

-Any death not related to chemotherapy/conditioning/immunosuppression regimen, progression of malignancy, or GVHD (only until day +100 post transplant)

-Any grade 4 or higher non-hematologic toxicity (not related to chemotherapy/conditioning/immunosuppression regimen, progression of malignancy, or GVHD) (Only until day +100 post transplant).

Deaths not related to chemotherapy/conditioning regimen/immunosuppression regimen, progression of malignancy, or GVHD be reported to the IRB within 24 hours of the Investigators knowledge of the occurrence and all other toxicities will be reported within 7 days of the Investigator's knowledge of occurrence.

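### The closed IRB reporting list in section 8.0 has no entry for a non-fatal SAE caused by a study procedure that is below grade 4 or hematologic

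*Combined protocol and SAP*

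**What the plan says.** Section 8.0 classifies an event as serious by outcome. One criterion is that it "requires inpatient hospitalization or prolongation of existing hospitalization", with no severity grade attached. The section notes that transplant patients are at high risk of adverse events and "often require multiple admissions to the hospital during the first 3-4 months after transplantation". It then restricts reporting: "For the purposes of this study, only the following SAE's will be reported to the IRB".

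Three entries follow:

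- failure of neutrophil engraftment by day 35;
- deaths not related to the treatment regimen, malignancy progression or GVHD, "only until day +100 post transplant";
- "Any grade 4 or higher non-hematologic toxicity", with the same exclusions and the same end date.

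The closing sentence gives 24 hours for the listed deaths and says that "all other toxicities will be reported within 7 days".

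Section 7.0 lists risks of the study itself. Among them: "Venipuncture, blood sampling, and catheter insertion can cause mild discomfort, bruising, and rarely infection" and "Repeated blood sampling can worsen anemia, which is monitored frequently after transplant". It says that toxicity attributed to the study will be graded by CTCAE version 5.0.

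Section 6.0 schedules two glucose tolerance tests (one with GLP-1 infusion, the other with microdialysis) and one clamp before transplant. All are repeated between days +80 and +100, with a tolerance of 10 days either side.

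**The concern.** The SAE definition turns on outcome, while the reporting list turns on grade, organ system and date. No entry turns on whether a study procedure caused the event. Some SAEs caused by the research can therefore meet the definition and match nothing on the list.

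The GLP-1 infusion, the clamp with arginine and the microdialysis are done for research. Harm from them is what an IRB most needs to see when it judges whether the procedures remain acceptable. Staff who follow section 8.0 as written would not be directed to send it.

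No aim, endpoint or analysis is affected. What is at stake is safety oversight.

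**Working it through.** The plan gives no figure to reproduce. The check sets the SAE definition against the list, then compares dates and counts visits.

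**1. Coverage.** Each case is hypothetical and assumed to be caused by a study procedure.

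| Event | SAE by definition? | List entry |
|---|---|---|
| Catheter-site infection below grade 4, leading to admission | Yes (hospitalization) | None |
| Anemia worsened by study sampling, prolonging a stay, non-fatal | Yes (hospitalization) | None at any grade, because the toxicity entry is non-hematologic |
| Serious grade 4 non-hematologic reaction by day +100 | Yes | Toxicity entry |
| Death by day +100 | Yes | Death entry |

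Engraftment failure is the only hematologic entry. It is a transplant outcome, so it does not help the second row. The death and toxicity entries have an end date but no stated start. Before transplant the gap is therefore one of grade and type, not of time.

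**2. Stated reasons.** Section 8.0 gives two: a high background risk of adverse events, and frequent admissions in the months after transplant. Both concern events that would occur without the study. Neither explains leaving out an event already attributed to a study procedure. The second is also limited to the period after transplant, whereas 3 of the 6 procedure visits come before it.

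**3. The closing sentence.** If the 7-day clause sets timing for the listed items, the gap stands. If it covers every other toxicity, it conflicts with the word that closes the list. The first reading is the more natural.

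**4. Dates.**

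- Tolerance added to both ends of the window: last permitted day is 100 + 10 = +110. Procedures on days +101 to +110 then fall after the day +100 cut-off, and even a procedure-related death there has no entry.
- Window read as day 90 with 10 days either side: 90 − 10 = 80 and 90 + 10 = 100. No procedure falls after the cut-off, but reporting closes on the day of a day +100 procedure.

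The literal text of section 6.0 supports the first reading, as does Appendix A, which applies the tolerance to a Day 80-100 column. The second is supported by section 1.0 (Subaims 1A and 1B), which places the repeat tests 90 days after transplant. Section 6.0 also puts total blood collection at about 110 days. Collection starts before chemotherapy, so a count from the first draw would end before day +110.

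**5. Exposure.** Section 10.1 recruits 40 patients: 34 plus 6 for dropout of about 10%. The ceiling is 40 × 6 = 240 procedure visits, of which 40 × 3 = 120 are before transplant. Assume that 4 (10% of 40) to 6 patients drop out, and that each completes 1 to 3 pre-transplant visits and none later:

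- 6 dropouts: before transplant 34 × 3 + 6 × 1 = 108 to 34 × 3 + 6 × 3 = 120; after, 34 × 3 = 102; total 210 to 222.
- 4 dropouts: before transplant 36 × 3 + 4 × 1 = 112 to 36 × 3 + 4 × 3 = 120; after, 36 × 3 = 108; total 220 to 228.

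The overall range is 210 to 228 visits. This counts opportunities for harm, not harm.

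**The case against.** A transplant cohort generates many serious events unrelated to the study, and a restricted list keeps the IRB from being flooded. The exclusions for regimen, malignancy and GVHD do not remove all of that background, so the grade limit does useful filtering. This stands, and it is why the list should be kept for events not attributed to the study.

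The procedure risks also look small. Section 7.0 calls infection rare. Research blood is not drawn at a known hematocrit below 24 before transfusion, and a nurse or physician is present on study days. Hypoglycemia is a weak example: recent diabetes therapy is an exclusion, the infusion accompanies oral glucose, and insulin is held on the morning of the post-transplant studies. Attributing anemia after transplant to study draws would be hard. All of this lowers the expected number of reports, but none of it is a route to the IRB. The Quality Assurance meeting in section 6.0 is likewise an internal review.

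Section 7.0 presupposes attribution to the study but describes no process for it. An added category must therefore say who attributes.

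A reader might infer more than the documents support:

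- *That such harm would never reach the IRB.* The IRB's own policy may require reporting and is not in the documents. Only the gap in this list is shown.
- *That the reasons for restriction have no force before transplant.* Only the admissions reason is limited in time; the general high risk of adverse events is not.
- *That ten days of procedures are certainly uncovered.* This depends on the literal tolerance. Even then, 10 of the 41 permitted days (+70 to +110) is a share of days, not of visits.
- *That data collection ends before the procedures do.* Section 6.0 ends prospective collection at day 100, but Appendix A marks data collection in the same column as the repeat procedures.

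**Conclusion.** The category gap holds on the text and depends on no reading of dates. A non-fatal SAE caused by a study procedure, if below grade 4 or hematologic, meets the protocol's own definition and has no entry on a list that calls itself complete. The wider reading of the 7-day clause does not rescue it, because it contradicts the closed list.

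The date gap is secondary and conditional. It is zero visits if the window means day 90 with 10 days either side. If procedures may run to day +110 it is an unknown share of the post-transplant visits, which number 102 to 108 under the dropout assumptions.

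The number of unreported events cannot be estimated. The point deserves an amendment because the remedy is specific and cheap and bears on participant safety. It does not threaten the scientific conclusions.

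**What to change.** 1. Add one category to section 8.0: any SAE that the investigator attributes to a study procedure (GLP-1 infusion, clamp with arginine, microdialysis, study blood draw), whatever its grade and including hematologic events. Keep the restricted list for all other events.
2. State that the 7-day timing applies to the listed items, including the new category, with listed deaths staying at 24 hours.
3. Reconcile sections 6.0 and 8.0 and Appendix A on the last permitted procedure day. Run reporting of study-attributed events until a stated time after each patient's last study procedure.

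The cost is a short amendment and a chart check after the last procedure for the patients who reach the repeat tests: 40 − 6 = 34 to 40 − 4 = 36 expected, 40 at most. There may also be a few extra IRB reports, a number the documents do not allow to be estimated. No dose, procedure or analysis changes.
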